### **3.3 Outcomes and Data Analysis**

Statistical analysis will be conducted with a biostatistician consultant. Continuous outcome variables will be summarized by the mean, median, standard deviation, minimum and maximum. Adverse effect data will be reported continuously, including all serious and non-serious adverse effects, as well as effects related to the surgical procedure and device-related.

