#### **4.1.1 Safety Endpoints**

The study safety endpoints will include a characterization of all adverse events (AE) for all participants, including those related to the implant surgical procedure, the implantable device,

and stimulation of patients with tetraplegia. In addition, these safety profile elements will be compared across the various phases of the study. Furthermore, patients with clinically significant complications related to surgery (hemorrhage, stroke, infection) will not undergo implantation or further participation in the study.

Participants may choose to withdraw from the study at any point, in addition, the study investigators may decide to conclude a patient's participation in the study for the following medical reasons:

- Onset of epilepsy;
- Significant decrement in neurological exam;
- Development of serious adverse events, physical or psychological, including negative behavioral symptoms, major depression, or suicidal ideation;
- Intra- or extra-cranial infection unresponsive to antibiotic treatment;
- Serious infection around the percutaneous connector unresponsive to antibiotic treatment;
- Development of intracranial hematoma requiring evacuation; and
- Need for urgent Magnetic Resonance Imaging (MRI) of any kind (brain or body).

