#### **4.1.3 Unanticipated Adverse Device Effects**

An unanticipated adverse device effect (UADE) is defined as any serious adverse effect on health or safety or any life-threatening problem or death caused by, or associated with the device [and/or stimulation therapy] if that effect, problem, or death that was not previously identified in nature, severity, or degree of incidence in the investigational plan or application (including a supplementary plan or application), or any other unanticipated serious problem associated with a device that relates to the rights, safety, or welfare of participants (21 CFR 812.3(s)).

Any UADE will result in an evaluation of that effect as soon as is possible, and will then be reported to the IRB within 10 days (OSU IRB policy v 12/19/16) and to the FDA within 10

working days after the sponsor-investigator first receives notice of the effect(s). [21 CFR 812.46(b), 812.150(a)(1), 812.150(b)(1)]

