#### **4.1.4 Documentation of Adverse Events**

All AEs from the time the study informed consent is signed through the time of device explantation will be recorded as AEs on the study adverse event log; each event being documented separately. Any adverse event occurring after this time and is considered related to the device or therapy by the Principal Investigator will be reported. AEs and SAEs will be followed until:

- AE is resolved and has returned to normal/baseline or has stabilized
- Subject has withdrawn from the study
- AE is judged by the investigator to be no longer clinically significant
- Study closure at which time, the responsibility for following any ongoing AEs will be transferred to the incoming clinical care team.

The Principal Investigator will serve as point of contact to which the team will report adverse events. All non-serious adverse events will be reported to the FDA and to The Ohio State University Institutional Review Board (IRB) during the annual reporting period.

Relatedness will be determined for all events according to the following criteria:

- **Definitely related:** The event is resolved by discontinuing stimulation and another cause cannot be identified.
- **Probably related:** The event resolves upon discontinuing stimulation and cannot be reasonably explained by the subject's current clinical state or any other cause.

- **Possibly related:** The event was likely caused by the subject's current clinical state, , however, the effect of stimulation cannot be ruled out.
- **Unlikely related:** The event did not occur temporally to stimulation and can be explained by the subject's current clinical state or any other cause.
- **Unrelated:** The event is explained by the subject's current clinical state or any other cause.

For purposes of determination of a UADE the following categories will be considered related: “definitely related” and “probably related”.

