#### **4.1.5 Reporting of Serious Adverse Events**

SAEs reported during the protocol defined reporting period per section 4.1.4 will be:

- Evaluated for their relatedness per section 4.1.4;
- Reported to the Data Safety Monitoring Committee;
- Included in the IRB Continuing Review; and
- Included in the FDA Annual Report.

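### The only adverse event relatedness scale counts an event as related for UADE purposes only if it resolves when stimulation stops, so array, connector, surgical, fatal and permanent events cannot qualify

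*Combined protocol and SAP*

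**What the plan says.** Section 4.1.4 applies one relatedness scale to all events.

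- *Definitely related*: "The event is resolved by discontinuing stimulation and another cause cannot be identified".
- *Probably related*: the event resolves when stimulation is discontinued, and neither the participant's clinical state nor anything else reasonably explains it.
- *Possibly related*: the clinical state is the likely cause, but an effect of stimulation remains open.
- *Unlikely related*: the timing does not fit stimulation and another explanation exists.
- *Unrelated*: "The event is explained by the subject's current clinical state or any other cause".

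The section then sets the gate: "For purposes of determination of a UADE the following categories will be considered related", and it names only the first two tiers. Section 4.1.5 sends serious adverse events to the same scale: "Evaluated for their relatedness per section 4.1.4". The documents give no second causality scale.

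Three other sections are wider. Section 4.1.3 defines a UADE by serious effects, life-threatening problems or death "caused by, or associated with the device [and/or stimulation therapy". Section 4.1.1 promises to characterise all adverse events, "including those related to the implant surgical procedure, the implantable device" and stimulation. Section 3.3 promises reporting of all adverse effects, "as well as effects related to the surgical procedure and device-related". After explantation, 4.1.4 narrows what is reported: "Any adverse event occurring after this time and is considered related to the device or therapy by the Principal Investigator will be reported".

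**The concern.** The scale asks one question: did the event go away when stimulation stopped? That suits a transient effect of the forearm stimulator. It does not suit the implant. Under section 4.5.2 the array records and a separate device stimulates. The array is placed by craniotomy (3.2.2), stays in for about 60 months of Phase III (3.2) and is used beyond its 30-day indication (Part III, section 7). The stimulator is external and comes off after each session (Part III, section 8), and section 4.5 classes it as non-significant risk. The scale is therefore built around the component the protocol treats as lower risk.

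Three things are at stake:

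- **Attribution.** Safety is a main product of a feasibility study of up to 5 participants, so one misattributed event alters the profile.
- **Expedited reporting.** Section 4.1.3 requires UADE reports to the IRB within 10 days and to the FDA within 10 working days. An unanticipated array effect, or a listed risk that exceeds its stated severity or incidence, could miss that route.
- **Possibly, events after explantation.** These are reported only if judged related. Section 4.2 lists risks of removal, and section 3.2.5 asks about neuropsychological decline after explant.

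**Working it through.** The plan gives no figure to reproduce; the check is one of definitions.

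**Inputs.** Five tiers and the UADE gate (4.1.4); three sources of adverse events, namely implant surgery, implantable device and stimulation (4.1.1); the UADE definition (4.1.3). Four of the five tier definitions mention stimulation. None mentions the device, array, connector or surgery.

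**Step 1: apply the tiers literally.** Cross the 3 sources with 2 outcomes on stopping stimulation: 3 × 2 = 6 combinations. Clinical state is taken to mean the participant's underlying condition.

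| Source | On stopping stimulation | Tiers that fit | Counts for UADE? |
|---|---|---|---|
| Surgery | resolves | *unrelated* (surgery is another cause) | no |
| Surgery | persists | *unrelated* | no |
| Array or connector | resolves | *unrelated* (the array is another cause) | no |
| Array or connector | persists | *unrelated* | no |
| Stimulation | resolves | *definitely*, *probably* | yes |
| Stimulation | persists | none | no |

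In the four surgery and array rows, *unlikely* also fits if the event is not close in time to stimulation. Result: 1 of 6 combinations reaches a counting tier, and 1 of 6 fits no tier.

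The last row fails every definition. The event does not resolve (tiers 1 and 2), the clinical state is not its likely cause (tier 3), its timing fits stimulation (tier 4), and it has no other cause (tier 5). A lasting burn from the sleeve is an example.

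**Step 2: a more generous reading.** Suppose another cause means only a cause outside the study. The surgery and array rows that resolve can then reach *probably related* or higher, giving 3 of 6. But the three rows that persist still fail tiers 1 and 2, and with no outside cause they now fit no tier at all, also 3 of 6. The resolution requirement alone keeps out every fatal or permanent event.

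**Step 3: set against the other sections.**

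- Death cannot resolve, so it can never count under 4.1.4, although 4.1.3 names it.
- A surgical event before the first session, or an event after explantation, has no stimulation to discontinue.
- Section 4.1.1 foresees connector infection, and section 4.2 answers an allergy to the implant by explantation. Neither turns on stopping stimulation.
- The word stimulation is not defined for the scale. Section 3.2.5 also uses it for intraoperative stimulation and transcranial magnetic stimulation.

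**Step 4: exposure, for scale only.** Section 3.2.3 allows up to 3 sessions a week of under 4 hours: 3 × 4 = 12 hours, and 12/168 = 7.1% of the week. Less about 30 minutes of setup per session, 3 × 3.5 = 10.5 hours, and 10.5/168 = 6.3%. The array is in place throughout, up to 5 × 60 = 300 participant-months with full enrolment and retention. Stimulation is thus stopped for most of every week as routine, so its stopping says little about the cause of an implant effect.

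**The case against.** The best reply is that little is lost in practice. All adverse events to explantation are logged. Serious ones go to the monitoring committee, IRB continuing review and the FDA annual report whatever their rating. Section 4.1.3 carries its own full definition and deadlines, and its closing clause, on other unanticipated serious problems linked to a device, does not use the relatedness test. An investigator following 4.1.3 would still report an unanticipated array effect. This limits the harm but does not remove the conflict: 4.1.4 states its gate without exception, and staff should not have to choose between two sections under a 10-day deadline.

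Four further points stand in part:

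- Section 4.1 already lists many surgical harms, including death, so many blocked events would not be UADEs unless they exceeded the stated severity or incidence. The hazard table in 4.5.1 also lists burns without a degree, so a severe burn may not be unanticipated. It would still fit no tier.
- The case report forms are an appendix not supplied here. The log may record source beside relatedness, which would ease the attribution problem but not the gate.
- The rule for events after explantation refers to device or therapy and to the investigator's judgement, and section 4.1 has participants evaluated until they exit the study. Whether the five-tier scale governs that judgement is inference.
- The 1-of-6 count and the 7.1% do not estimate how many events would be misclassified. An effect of the array and stimulator acting together might resolve when stimulation stops.

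**Conclusion.** The concern holds. Section 4.1.4 conflicts with the UADE definition in 4.1.3 and cannot properly supply the attribution promised in 3.3 and 4.1.1. Followed as written, it gives wrong classifications; this is not merely missing detail. Read literally, 1 of 6 source-by-outcome combinations can count as related for a UADE; on the more generous reading it is 3 of 6. On either reading no fatal or permanent event can count, and a lasting stimulation injury has no tier. The conclusion rests on the wording alone and on there being no second scale in the documents. How many events would be affected cannot be estimated from them. The consequence is misattribution and possible loss of expedited reporting, not loss of recording.

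**What to change.** Rewrite the relatedness part of 4.1.4 as follows.

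1. Rate each adverse event separately for relatedness to (a) the implant or explant procedure, (b) the array and percutaneous connector, and (c) the stimulator and neuromuscular stimulation. Other study procedures can be added if wanted.
2. Judge by timing and plausible mechanism. Use resolution on stopping stimulation only as supporting evidence for (c), never as a condition, so that fatal and permanent events can be rated.
3. Define stimulation for this purpose.
4. Let the UADE gate cover *definitely* or *probably related* to any device component, including effects associated with its implantation or removal, in line with 4.1.3.
5. Apply the same definitions to events after explantation.
6. Tabulate adverse events by source, to deliver what 3.3 and 4.1.1 promise.

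A narrower repair would drop the resolution requirement and add the device to the tier definitions. That would reconcile 4.1.3 and 4.1.4 but would not by itself separate surgical from device effects.

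The cost is protocol wording and possibly new log fields, with slightly more events rated related. Section 3.2.3 describes work already under way with a participant, so any existing ratings should be revisited. No extra participants or procedures are needed.

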#### **4.1.5 Reporting of Serious Adverse Events**

SAEs reported during the protocol defined reporting period per section 4.1.4 will be:

- Evaluated for their relatedness per section 4.1.4;
- Reported to the Data Safety Monitoring Committee;
- Included in the IRB Continuing Review; and
- Included in the FDA Annual Report.

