## **4. Risk Analysis**

### **4.1 Risks**

The surgical risks for implantation are the same as for any intracranial craniotomy, image guided procedures and implantable device such as a deep brain stimulator or a motor cortex stimulator procedure. This includes hemorrhages (intraparenchymal, subdural or epidural hematoma), paralysis, coma and/ or death, stroke, leaking of fluid surrounding the brain, seizures, infection, allergic reaction, temporary or permanent neurological complications, confusion or attention problems, pain at the surgery sites and headaches.

Training and therapeutic sessions involving BCI regulated functional electrical stimulation will need to be monitored for autonomic dysreflexia signs and symptoms.

As with any muscle stimulator, there can be a risk of excessive current and skin irritation or burns. The stimulator in the Neural Bridging System, however, limits the average output current density to less than  $2\text{mA/cm}^2$  at the skin and the average power density to less than  $0.25\text{W/cm}^2$  to provide safe levels and avoid tissue damage. Despite these built-in safety limits, current and power density could exceed FDA guidelines if electrodes lift off the skin. This has the potential to cause causing minor irritation or first degree burns locally. The research investigator will monitor frequently during test sessions for wrinkles and misalignment of the sleeve, and any signs of electric shock, skin irritation, and/or burns.

The sleeve material itself is spandex, with registration marks printed on it. The material itself has been formally tested for biocompatibility, both in vitro and in vivo, prior to printing and laundering. The printed, laundered sleeve was tested in Battelle's IRB-approved Able-bodied study for up to 8 hours, with and without similar nontoxic conductive lotion. No adverse skin

reactions were observed. The investigator, who will already be monitoring frequently for signs of irritation from electric shock, will also monitor for signs of allergic skin reaction.

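### The relatedness scale in 4.1.4 recognises only stimulation, so surgical and implant harm cannot ordinarily reach the UADE clock and falls to an SAE route with no stated time limit for the DSMC or IRB

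*Combined protocol and SAP*

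**What the plan says.** Section 4.1.5 gives four steps for a serious adverse event (SAE). It is graded for relatedness under 4.1.4 and then goes to three bodies:

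- DSMC: "Reported to the Data Safety Monitoring Committee", with no time limit.
- IRB: "Included in the IRB Continuing Review; and", with no interval stated.
- FDA: "Included in the FDA Annual Report".

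Non-serious events go to the FDA and IRB "during the annual reporting period" (4.1.4).

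The only reporting clock is in 4.1.3. A UADE is to be "reported to the IRB within 10 days (OSU IRB policy v 12/19/16) and to the FDA within 10" working days. A UADE is a serious effect caused by or associated with the device or the stimulation, and one "that was not previously identified in nature, severity, or degree of incidence in the investigational plan". A residual clause adds other unanticipated serious problems associated with a device.

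Section 4.1.4 has five relatedness grades. Probably related reads "The event resolves upon discontinuing stimulation and cannot be reasonably explained" by the participant's clinical state or another cause. Definitely related likewise needs the event to be resolved by stopping stimulation, with no other cause found. Only these two grades count when deciding whether an event is a UADE.

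Section 4.1 lists the known surgical risks: "This includes hemorrhages (intraparenchymal, subdural or epidural hematoma), paralysis, coma and/ or death, stroke", and later seizures and infection. It gives no incidence for them. Section 4.1.1 includes events from the implant operation, the implanted device and stimulation in the safety endpoints. Section 3.3 says adverse effect data, including surgical and device-related effects, will be reported on a continuous basis. It names no recipient and no deadline.

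**The concern.** The trial's gravest hazards come from a craniotomy and a percutaneous cortical implant. The causality scale asks only about a surface stimulator worn on the arm. An event is graded as related in the sense that matters for rapid reporting only if switching off that stimulator makes it go away.

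This is more than missing detail. It is a stated rule that gives the wrong answer for a class of events the protocol itself puts in its safety endpoints. Two things are at stake:

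- **Independent review.** The DSMC is to advise on the continuing safety of enrolled participants (5.1). The text sets no limit on how long it, or the IRB, may wait to hear of a serious surgical or implant event.
- **The safety analysis.** Sections 3.3 and 4.1.1 promise results on surgery-related and device-related events, compared across phases. The relatedness grade cannot supply that attribution.

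**Working it through.** The plan states no figure that bears on this point, so the check is to trace events through the text.

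**Step 1. What the UADE clock requires.** Reading 4.1.3 and 4.1.4 together, an event must be (a) serious and associated with the device or stimulation, (b) not already identified in nature, severity or degree of incidence, and (c) graded definitely or probably related. Condition (c) adds that the event resolves when stimulation is discontinued.

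**Step 2. A fatal bleed at implantation.** Surgery is Phase II and stimulation belongs to Phase III (3.2), so there may have been no study stimulation to stop. A fatal event cannot resolve in any case, so (c) fails. Condition (b) probably fails too, because haemorrhage and death are listed in 4.1. Since surgery is another cause, the scale points toward unlikely related or unrelated.

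**Step 3. An infection at the percutaneous connector.** There is no evident reason for it to clear when a surface stimulator is switched off, so (c) ordinarily fails. Infection is also a listed risk, so (b) probably fails.

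**Step 4. A serious implant harm that nobody listed.** Conditions (a) and (b) are met, and this is what 4.1.3 is meant to catch. Unless the harm happens to resolve when stimulation stops, (c) still fails. This case shows that the fault lies in the 4.1.4 scale and does not depend on how complete the 4.1 risk list is.

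**Step 5. A stimulation harm, for contrast.** A serious event during a session that ends when stimulation stops can pass (c). The scale works for the source it was written for.

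**Step 6. Where Steps 2 to 4 lead.** All three go to 4.1.5: the DSMC with no limit, the IRB at an unstated interval, and the FDA annually.

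**Step 7. Whether other text repairs this.**

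- Section 3.3 promises continuous reporting, but without a recipient or deadline it sets no clock. It also sits badly with the annual route.
- Section 5.1 has the DSMC evaluate accumulating data, but gives no meeting schedule or expedited trigger.
- Section 4.1.1 ends participation for a person with a clinically significant surgical complication. It says nothing about when independent bodies are told.

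**Scale.** Enrolment is up to 5 (3.1). One affected participant is at least 1/5 = 20% of the sample.

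**The case against.** Several points against this carry weight.

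- **The UADE definition is broader than the listed-risk argument suggests.** It covers severity and degree of incidence as well as nature, and it has a residual clause. Because 4.1 gives no surgical incidence, whether a given bleed was anticipated in degree can be argued either way. This stands, so the not-previously-identified test is only a likely barrier. It does not remove the 4.1.4 barrier, which applies to any UADE determination.
- **Some implant-era events could qualify.** A seizure during a session might end when stimulation stops. This stands, and is why the point says cannot ordinarily.
- **SAEs do get something extra.** Reporting to the DSMC is a separate step that non-serious events lack, and the Principal Investigator is the contact for all adverse events. Someone sees the event. What is missing is a time limit for independent review.
- **Faster rules may exist elsewhere.** Sections 4.1.2 and 4.1.3 cite an IRB policy that is not in the documents, and 4.1.5 does not invoke it for SAE timing. The protocol also binds the study to federal regulations. I did not have the Part III pages on investigator agreements and IRB information. The finding is about the protocol text, not about what the site would do.

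A reader might go further and infer that a fatal haemorrhage would wait up to a year before anyone independent saw it. The documents do not support that. The DSMC report has no deadline, which is not the same as a late one. The IRB interval is unstated, and only the FDA report is explicitly annual.

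**Conclusion.** The concern holds as a conflict between sections. Section 4.1.3 defines a UADE by association with the device, and 4.1.1 counts surgical and implant events as safety endpoints. The scale in 4.1.4 nevertheless keeps those events out of the grades that start the UADE clock, unless they happen to resolve when stimulation stops. They then take the 4.1.5 route, which gives no time limit to the DSMC, no stated interval to the IRB and an annual report to the FDA.

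The conclusion rests on applying 4.1.4 as written and on no shorter clock being imported from the uncited parts of the IRB policy or from regulation. The consequence in days cannot be derived from the documents, so none is claimed. The protocol should be corrected. The change is specific and small, and it matters because each serious event is a large share of the evidence in a study of up to 5 people.

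**What to change.** 1. **Section 4.1.4.** Grade relatedness separately for the surgical procedure, the implanted device and stimulation. Require resolution on stopping stimulation only for the stimulation grade. Let a definite or probable grade for the implanted device or for stimulation count toward a UADE. Unanticipated implant harm then falls under the existing IRB and FDA clocks.
2. **Section 4.1.5.** State a time limit for reporting to the DSMC and IRB every SAE at least possibly related to surgery, implant or stimulation, including anticipated ones. The 10 days that 4.1.3 already sets for the IRB would serve. Keep the periodic summaries. Anticipated SAEs would still reach the FDA through the annual report unless the sponsor-investigator chooses otherwise.
3. **Reconcile 3.3, 4.1.1, 4.1.3, 4.1.4 and 4.1.5.** In particular, say to whom and how often the continuous reporting in 3.3 is made. If the cited IRB policy already sets an SAE clock, state it in 4.1.5.

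The cost is a few sentences, two further relatedness fields on the adverse event log, and some additional expedited reports. The number of those reports is unknown because the documents give no SAE rate. Restricting the clock to events at least possibly related leaves out unrelated hospitalisations over the roughly 60 months of Phase III.
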